8.4.8. Adverse Events of Special Interest

Not applicable.

8.4.8.1. Lack of Efficacy

The investigator must report signs, symptoms, and/or clinical sequelae resulting from lack of efficacy. Lack of efficacy or failure of expected pharmacological action is reportable to Pfizer Safety **only if associated with an SAE**.

8.4.9. Medical Device Deficiencies

Medical devices being provided for use in this study are those listed in [Section 6.1.2](#). In order to fulfill regulatory reporting obligations worldwide, the investigator is responsible for the detection and documentation of events meeting the definitions of device deficiency that occur during the study with such devices.

The definition of a medical device deficiency can be found in [Appendix 8, Section 10.8](#).

Note: AEs and/or SAEs that are associated with a medical device deficiency will follow the same processes as other AEs or SAEs, as outlined in [Sections 8.4.1 through 8.4.4](#) and [Appendix 3, Section 10.3](#) of the protocol.

8.4.9.1. Time Period for Detecting Medical Device Deficiencies

Medical device deficiencies that result in an incident will be detected, documented, and reported during all periods of the study in which the medical device is used.

Importantly, reportable device deficiencies are not limited to problems with the device itself but also include incorrect or improper use of the device and even intentional misuse, etc.

If the investigator learns of any device deficiency at any time after a participant has been discharged from the study, and such deficiency is considered reasonably related to a medical device provided for the study, the investigator will promptly notify the sponsor.

The method of documenting medical device deficiencies is provided in [Appendix 8, Section 10.8](#).

8.4.9.2. Follow-Up of Medical Device Deficiencies

Follow-up applies to all participants, including those who discontinue study intervention.

The investigator is responsible for ensuring that follow-up includes any supplemental investigations as indicated to elucidate the nature and/or causality of the deficiency.

New or updated information will be recorded on a follow-up form with all changes signed and dated by the investigator.

8.4.9.3. Prompt Reporting of Device Deficiencies to the Sponsor

When a device deficiency occurs:

- 1 The investigator notifies the sponsor by telephone or email within 1 business day of determining that the incident meets the protocol definition of a medical device deficiency.
- 2 The device deficiency must be recorded on the Medical Device Complaint form.
- 3 If an AE (either serious or nonserious) associated with the device deficiency occurs, then the AE must be entered into the AE section of the CRF.
- 4 If an SAE associated with the device deficiency is brought to the attention of the investigator, the investigator must immediately notify Pfizer Safety of the SAE (see [Section 8.4.1.1](#)). All relevant details related to the role of the device in the event must be included in the CT SAE Report Form as outlined in [Sections 8.4.1.1](#) and [8.4.1.2](#).

The sponsor will be the contact for the receipt of device deficiency information.

8.4.9.4. Regulatory Reporting Requirements for Device Deficiencies

The investigator will promptly report all device deficiencies occurring with any medical device provided for use in the study in order for the sponsor to fulfill the legal responsibility

to notify appropriate regulatory authorities and other entities about certain safety information relating to medical devices being used in clinical studies.

The investigator, or responsible person according to local requirements (eg, the head of the medical institution), will comply with the applicable local regulatory requirements relating to the reporting of device deficiencies to the IRB/EC.

8.4.10. Medication Errors

Medication errors may result from the administration or consumption of the study intervention by the wrong participant, or at the wrong time, or at the wrong dosage strength.

Medication errors are recorded and reported as follows:

Recorded on the Medication Error Page of the CRF	Recorded on the Adverse Event Page of the CRF	Reported on the CT SAE Report Form to Pfizer Safety Within 24 Hours of Awareness
All (regardless of whether associated with an AE)	Any AE or SAE associated with the medication error	Only if associated with an SAE

Medication errors include:

- Medication errors involving participant exposure to the study intervention;
- Potential medication errors or uses outside of what is foreseen in the protocol that do or do not involve the study participant.

Such medication errors occurring to a study participant are to be captured on the medication error page of the CRF, which is a specific version of the AE page.

Whether or not the medication error is accompanied by an AE, as determined by the investigator, the medication error is recorded on the medication error page of the CRF and, if applicable, any associated AE(s), serious and nonserious, are recorded on the AE page of the CRF.

In the event of a medication dosing error, the sponsor should be notified within 24 hours.

Medication errors should be reported to Pfizer Safety within 24 hours on a CT SAE Report Form **only when associated with an SAE**.

8.5. Pharmacokinetics

Blood samples of approximately 3 mL, to provide a minimum of 1.2 mL plasma, will be collected for measurement of plasma concentrations of isavuconazole as specified in the [SoA](#). Instructions for the collection and handling of biological samples will be provided in the laboratory manual or by the sponsor. The actual date and time (24-hour clock time) of each sample will be recorded.

The actual times may change, but the number of samples will remain the same. All efforts will be made to obtain the samples at the exact nominal time relative to dosing. Unless stated in [Section 1.3.1](#), collection of samples up to and including 10 hours after dose administration that are obtained within 10% of the nominal time relative to dosing (eg, within 6 minutes of a 60-minute sample) will not be captured as a protocol deviation, as long as the exact time of the collection is noted on the source document and data collection tool (eg, CRF/DCT). Collection of samples more than 10 hours after dose administration that are obtained ≤ 1 hour away from the nominal time relative to dosing will not be captured as a protocol deviation, as long as the exact time of the collection is noted on the source document and data collection tool (eg, CRF/DCT).

Samples will be used to evaluate the PK of isavuconazole. Samples collected for analyses of isavuconazole (plasma) concentration may also be used to evaluate safety or efficacy aspects related to concerns arising during or after the study, for metabolite identification and/or evaluation of the bioanalytical method, or for other internal exploratory purposes.

Genetic analyses will not be performed on these plasma samples. Participant confidentiality will be maintained.

Samples collected for measurement of plasma concentrations of isavuconazole will be analyzed using a validated analytical method in compliance with applicable SOPs.

The PK samples must be processed and shipped as indicated in the instructions provided to the investigator site to maintain sample integrity. Any deviations from the PK sample handling procedure (eg, sample collection and processing steps, interim storage or shipping conditions), including any actions taken, must be documented and reported to the sponsor. On a case-by-case basis, the sponsor may make a determination as to whether sample integrity has been compromised.

Any changes in the timing or addition of time points for any planned study assessments must be documented and approved by the relevant study team member and then archived in the sponsor and site study files, but will not constitute a protocol amendment. The IRB/EC will be informed of any safety issues that require alteration of the safety monitoring scheme or amendment of the ICD.

8.6. Genetics

Genetics (specified analyses) are not evaluated in this study.

8.7. Biomarkers

Biomarkers are not evaluated in this study.

8.8. Immunogenicity Assessments

Immunogenicity assessments are not included in this study.

8.9. Health Economics

Health economics/medical resource utilization and health economics parameters are not evaluated in this study.

9. STATISTICAL CONSIDERATIONS

Detailed methodology for summary and statistical analyses of the data collected in this study is outlined here and further detailed in the SAP, which will be maintained by the sponsor. The SAP may modify what is outlined in the protocol where appropriate; however, any major modifications of the primary endpoint definitions or their analyses will also be reflected in a protocol amendment.

9.1. Statistical Hypotheses

No formal statistical hypothesis testing will be conducted for efficacy analysis.

9.1.1. Estimands

9.1.1.1. Estimand for treatment emergent adverse event (TEAE)

The incidence rates of TEAEs by SOC and PT will be summarized without regard to adherence to the isavuconazole treatment and use of prohibited medication.

9.1.1.2. Estimand for the all-cause mortality

The percentage of all-cause mortality on Day 42 and 84 will be estimated in participants with IFD caused by *Aspergillus* species and other filamentous fungi, or Mucormycosis without regard to adherence to the isavuconazole treatment.

9.1.1.3. Estimand for the overall, clinical, mycological, and radiological responses

The crude rate of overall response, clinical response, mycological response, and radiological response at EOT, Day 42, and Day 84 will be estimated in participants with IFD caused by *Aspergillus* species and other filamentous fungi, or Mucormycosis while participants are on the isavuconazole treatment. Data collected after use of the prohibited medications will not be used. Participants who are not available for clinical, mycological or radiological responses will be considered as a failure for overall response.

9.2. Analysis Sets

For purposes of analysis, the following analysis sets are defined:

Defined Analysis Set	Description
Enrolled	"Enrolled" means a participant's, or their legally authorized representative's, agreement to participate in a clinical study following completion of the informed consent process and assignment to study intervention. A participant will be considered enrolled if the informed consent is not withdrawn prior to participating in any study activity after screening. Potential participants who are screened for the purpose of determining eligibility for the study, but do not participate in the study, are not considered enrolled, unless otherwise specified by the protocol.
ITT	The ITT population consists of all enrolled participants who receive at least 1 dose of study intervention. The ITT is the primary efficacy population.
mITT	The mITT population consists of ITT participants who had proven or probable IFD as determined by the investigators based on the definition specified in Appendix 9, Section 10.9 .
myITT-IA	The myITT-IA population consists of mITT participants with proven or probable IA based on cytology, histology, culture, or GM and assessed by the investigators.
myITT-IM	The myITT-IM population consists of mITT participants with proven or probable IM based on cytology, histology, culture, or GM and assessed by the investigators.
Safety Population	The safety population consists of all enrolled participants who receive at least 1 dose of study intervention.
PK Concentration Analysis Set	All participants who are treated and have at least 1 measurable PK concentration data, and who have no major protocol violations that can have an effect on their PK data.

9.3. Statistical Analyses

The SAP will be developed and finalized before database lock and will describe the analyses and procedures for accounting for missing, unused, and spurious data. This section is a summary of the planned statistical analyses of the primary and secondary endpoints.

9.3.1. Efficacy Analyse

No formal statistical hypothesis testing will be conducted for efficacy analyses.

The key secondary efficacy endpoint of crude rate of all-cause mortality through Day 42 will be analyzed on the ITT population. Any death that occurs after first dose of study intervention through Day 42 will be included. A participant with the last known survival status before Day 42 or missing and the last assessment day before Day 42 will be treated as death. The 95% CI of the crude mortality rate will be calculated based on an exact binomial distribution.

The same analysis will be repeated for the mITT, myITT-IA, and myITT-IM populations.

All-cause mortality rate over time by Day 42 will also be estimated using the KM method. In the KM analysis, time to death will be observed until Day 84 for participants with IA and Day 180 for participants with IM.

The other secondary endpoint of the percentage of all-cause mortality through Day 84 will be summarized and analyzed similarly to the all-cause mortality through day 42.

The clinical, mycological, radiological, and overall response at EOT, Day 42 and Day 84 will be summarized. The 95% CIs of the response rates will be calculated based on an exact binomial distribution.

9.3.2. Safety Analyses

Safety variables will be summarized descriptively for the safety population. 95% CIs for the binary outcome of selected safety variables may be presented based on an exact binomial distribution.

The primary safety endpoint is the incidence rates of TEAEs by SOC and PT. A TEAE is defined as any AE that starts on or after the first administration of study intervention until 28 days after last dose of study intervention. Other key summaries of AEs include the summaries of

- TEAE related to study intervention
- Treatment-Emergent SAEs
- TEAE leading to discontinuation of study intervention
- TEAE leading to deaths
- All deaths

Vital signs will be listed and summarized by means and standard deviation (SD). Laboratory test values will be presented in change from baseline and shift tables and by individual listings with flagging of values outside the normal reference ranges. ECG findings will be presented by listings and frequency tables, as appropriate.

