2.3.1. Risk Assessment

Important Identified and Important Potential Risk of Clinical Significance	Summary of Data/Rationale for Risk	Mitigation Strategy
Study Intervention(s) Isavuconazonium sulfate		
Important identified and important potential risks for isavuconazole include the following: 
 • Important identified risks: side-effects during the isavuconazole infusion (Infusion-related reactions) • Important potential risks: teratogenicity 	The potential risks are based on product labeling for isavuconazole and are common with the triazole class.	Eligibility criteria have been selected to ensure that only appropriate participants are included in the study (see Section 5).
Study Procedures		
Participants will be expected to commit time and may experience some discomfort while undergoing study assessments.		

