8.3.2. Vital Signs

Assessments comprising blood pressure (SBP and DBP; mmHg), PR(bpm), RR(times per minute) and axillary, ear, or forehead BT(C°) will be made at Screening and visits as specified in [SoA](#). If participants discontinue from study intervention prior to Day 7, Day 7 and Day 14 assessments on vital signs are not required. At the Follow-up visit, vital signs assessments will be performed only in participants with abnormalities observed at the previous visit.

On Day 1, vital signs will be measured within 1 hour before and 1 hour after the end of each dose of study intervention administration. From Day 7 onwards, vital signs will be measured once prior to study intervention administration.

Any untoward vital sign findings that are identified during the active collection period and meet the definition of an AE or SAE ([Appendix 3, Section 10.3](#)) must be reported according to the processes in [Sections 8.4.1 to 8.4.3](#).

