6.6.3. Vital Signs

Vital signs including systolic and diastolic blood pressures (mmHg), and PR (bpm) will be descriptively summarized for actual values and change from baseline to post-baseline time-points. For the change values, participants with both values at baseline and each respective time-point for calculating the change will be included. Participants who have both baseline and at least one post-baseline will be included in this summary.

Respiratory rate and temperature data collected during the study will be considered source data and will not be reported.

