Appendix 3. Analysis window for efficacy and safety endpoints

Investigator Assessments	Visits	Scheduled Day	Window in Days
Clinical and Mycological	Day 42	42	2 to 49
	Day 84	84	50 to 91
	Day 126	126	92 to 133
	Day 168	168	134 to 175
Radiological	Day 42	42	8 to 49
	Day 84	84	50 to 91
	Day 126	126	92 to 133
	Day 168	168	134 to 175
Clinical, Mycological and Radiological	EOT	Last Dose Day	Closest to Last Dosing Day

Safety Assessments	Visits	Scheduled Day	Window in Days
Laboratory Tests for both IA and IM	Day 1	1	1
	Day 7	7	2 to 9
	Day 14	14	10 to 20
	Day 28	28	21 to 34
	Day 42	42	35 to 63
	EOT	Last Dose Day	Closest to Last Dosing Day
	Follow Up	Nominal Follow up Visit	NA
Laboratory Tests for IM	Day 84	84	64 to 105
	Day 126	126	106 to 147
	Day 168	168	148 to 201

Safety Assessments	Visits	Scheduled Day	Window in Days
Vital Signs for both IA and IM	Day 1	1	Using CRF Day/Time
	Day 7	7	2 to 9
	Day 14	14	10 to 28
	Day 42	42	29 to 63
	Day 84	84	64 to 105
	EOT	Last Dose Day	Closest to Last Dosing Day
	Follow Up [#]	Nominal Follow up Visit	NA
Vital Signs for IM	Day 126	126	106 to 147
	Day 168	168	148 to 201
ECG for both IA and IM	Day 1	1	1
	Day 7	7	2 to 9
	Day 14	14	10 to 28
	Day 42	42	29 to 63
	Day 84	84	64 to 105
	EOT	Last Dose Day	Closest to Last Dosing Day
	Follow Up [#]	Nominal Follow up Visit	NA
ECG for IM	Day 126	126	106 to 147
	Day 168	168	148 to 201

[#] Only in participants with abnormalities observed at EOT.

If more than one observation exists within the analysis window, the observation closest to the scheduled visit day will be selected for that visit. If there are two observations that have the same distance from the scheduled day, the value that is after the scheduled day will be selected in the analysis. If more than one observation are made on the same day, an average value if continuous or the worst value if categorical will be included in the analysis. The Follow Up visit will use the nominal follow-up visit with no windows defined.

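### Day 1 vital signs are taken before and after each dose, but no planned table pairs them by dose or counts participants with a marked change, so the tables are insensitive to an uncommon infusion-related reaction.

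*Protocol*

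**What the plan says.** Protocol 2.3.1 names one important identified risk: "side-effects during the isavuconazole infusion (Infusion-related reactions)". The other entry there, teratogenicity, is classed as potential.

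Protocol 8.3.2 says that on Day 1 "vital signs will be measured within 1 hour before and 1 hour after the end of each dose". After that, "From Day 7 onwards, vital signs will be measured once prior to study intervention administration". Loading is three doses per 24 hours, IV or oral (Protocol 6.1.1), so Day 1 can hold up to three before/after pairs, or six reading times.

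On analysis, Protocol 9.3.2 says "Vital signs will be listed and summarized by means and standard deviation (SD)". SAP 6.6.3 says that systolic and diastolic pressure and pulse "will be descriptively summarized for actual values and change from baseline". SAP 3.5.3 sets the baseline as the Day 1 value before dosing. SAP 5.2.2 gives n, mean, SD, median, minimum and maximum for continuous data.

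SAP Appendix 3 has a general rule for repeated readings: "If more than one observation are made on the same day, an average value if continuous". In the same appendix, Day 1 vital signs are assigned by the day and time on the CRF, whereas Day 1 laboratory tests and ECG simply have a one-day window.

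For comparison, SAP 6.6.2 counts participants crossing limits for liver tests and creatinine, and SAP 6.6.4 does so for QTcF. SAP 6.6.3 has no such count.

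**The concern.** The Day 1 schedule resembles a design for detecting acute effects of dosing, but the analysis does not use it that way. Change is measured from a single value before the first dose. A fall after the second or third dose is therefore mixed with whatever drift has occurred since the morning in an acutely ill patient. Nothing reports how many participants had a marked change across a dose.

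An acute reaction would be expected in a few participants, and a group mean barely responds to a few participants. Vital signs are a named secondary safety variable, so the study report could carry a table showing essentially no change while some individuals reacted. If the same-day averaging rule also covers Day 1, pre-dose and post-dose readings are pooled and the contrast is lost within each participant as well.

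**Working it through.** **The plan's own figure.** Protocol 9.5 gives an 86.6% chance of seeing at least one case of a 3% event in 66 treated participants. 1 − 0.97^66 = 1 − 0.134 = 0.866, so it reproduces. A 3% event means about 2 of 66 participants (0.03 × 66 = 1.98). The calculation below uses 2 of 66.

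**Assumptions.** The documents give no SD for vital signs and no rate for infusion reactions. I assume a 30 mmHg systolic fall after one dose (range 20 to 40), an SD of 10 to 20 mmHg for the quantity averaged, and all 66 contributing.

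**Shift in a time-point mean** = (participants affected × fall) / 66.
- 2 × 30 / 66 = 0.91 mmHg
- 2 × 20 / 66 = 0.61 mmHg; 2 × 40 / 66 = 1.21 mmHg

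**Standard error of the mean** = SD / √66.
- SD 10: 1.23 mmHg; SD 15: 1.85 mmHg; SD 20: 2.46 mmHg

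For each of these falls the shift is below even the smallest standard error. At 10% incidence the shift is 0.10 × 30 = 3.0 mmHg, which exceeds the standard error. The insensitivity therefore concerns uncommon reactions.

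**If Day 1 readings are averaged.** A fall in one of six readings lowers that participant's Day 1 average by 30 / 6 = 5 mmHg. Over the five readings after baseline it is 30 / 5 = 6 mmHg.
- Group mean, six readings: 2 × 5 / 66 = 0.15 mmHg
- Group mean, five readings: 2 × 6 / 66 = 0.18 mmHg
- At 10% incidence, six readings: 0.10 × 5 = 0.5 mmHg

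Averaging also weakens the minimum, because the extreme then shows 5 or 6 mmHg in place of 30.

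**What a count would give** (exact binomial, n = 66):

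| Participants meeting the criterion | Rate | 95% CI |
|---|---|---|
| 0 | 0% | 0 to 5.4% |
| 2 | 3.0% | 0.4 to 10.5% |
| 7 | 10.6% | 4.4 to 20.6% |

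A count carries information at the incidence the trial was sized for, where the mean does not.

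**The case against.** The strongest reply is that the primary endpoint already covers this risk. Treatment-emergent adverse events are tabulated by SOC and PT, with severity, relatedness, seriousness and discontinuation (SAP 6.1 and 6.6.1). Protocol 8.3.2 requires untoward vital-sign findings that meet the adverse event definition to be reported, and SAP 3.5.1 covers abnormalities that cause symptoms, need intervention or are judged clinically significant. An infusion reaction is also a clinical diagnosis, not a blood-pressure cut-off. All of this stands. A reported reaction will be counted, and at 3% incidence it has an 86.6% chance of appearing at least once. But that route depends on investigator judgement in an open-label study, no event of special interest is defined (Protocol 8.4.8), and the scheduled readings are the objective cross-check.

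A reader might infer that vital signs are analysed only as means and that the data cannot show a reaction. The documents do not support that. Protocol 9.3.2 promises a listing, and SAP 5.2.2 gives the minimum and maximum. Unless Day 1 is averaged, a large fall should appear in both. Neither says how many participants were affected.

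A reader might also take Day 1 averaging as settled. It is not. The CRF day-and-time entry and the pre-dose baseline both suggest that the readings are kept apart, but the SAP does not say so.

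Nor is the omission of respiratory rate and temperature an inconsistency in reporting. SAP 6.6.3 says "Respiratory rate and temperature data collected during the study will be considered source data and will not be reported", and Protocol 8.3.2.2 treats them the same way unless otherwise noted. Reporting them would need new eCRF fields, and I do not ask for it.

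Finally, with no comparator, some threshold crossings will reflect the illness. That is true. Pairing within participant and dose reduces the problem but does not remove it.

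**Conclusion.** The point holds as a moderate gap in safety reporting. The planned tables do not use the only scheduled before/after-dose contrast, and they are insensitive to an uncommon acute reaction: about 0.9 mmHg (0.6 to 1.2 for falls of 20 to 40 mmHg) against a standard error of 1.2 to 2.5 mmHg. If the averaging rule applies to Day 1, the shift for a 30 mmHg fall is about 0.15 to 0.2 mmHg. The sizes rest on the assumed fall, SD and 2 affected of 66. The absence of a per-dose change and of a participant count does not depend on those assumptions.

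There are two limits. Loading may be oral, so fewer than 66 participants may contribute to an infusion-specific summary, and its interval would then be wider. The post-dose reading comes after the infusion ends, so a change that has already resolved will not be captured by any analysis of these data. Neither the sample size nor the primary endpoint is affected.

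**What to change.** Amend SAP 6.6.3 and Appendix 3, and align Protocol 9.3.2:

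1. State that Day 1 vital signs are kept by dose and by pre-dose or post-dose time, and are exempt from the same-day averaging rule. The averaging of three blood-pressure readings at each time (Protocol 8.3.2.1) is a separate matter and can stay.
2. Summarise post-dose minus pre-dose change in systolic pressure, diastolic pressure and pulse for each Day 1 dose, split by IV and oral route.
3. Report n (%) of participants, with exact 95% CI, who meet numerical change criteria at any Day 1 dose. The sponsor should write the criteria into the SAP before the interim snapshot.

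The split by route needs route in the database. Protocol 6.1.1 treats route as source data that need not be reported there, while SAP 6.5.4 summarises IV and oral duration separately. The two passages must be reconciled.

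The cost is SAP wording and one extra table. Blood pressure and pulse need no new measurements. If route is not already captured, it needs a field and back-entry for participants already enrolled. The table should carry a note that some crossings will reflect the underlying illness.
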